## 4 Statistical Methodology

#### 4.1 Planned Analyses

All statistical processing will be performed using statistical analysis software (SAS®) unless otherwise stated. Safety analyses will be performed using the safety population.

Continuous data will be summarized with sample size (N), mean, median, standard deviation, minimum and maximum. Categorical data will be summarized with N, frequency counts, and percentages, based on N.

#### 4.2 Disposition of Subjects

The number of subjects in the Safety Population, who completed the study and the reasons for any premature discontinuation from the study, will be presented. Listings will indicate whether subjects met all inclusion and exclusion criteria, and, if not, which criteria were not met.

A summary and a listing of protocol deviations will be presented.

### 4.3 Baseline and Demographic Characteristics

Subject baseline and demographic characteristics, including age, race, ethnicity, and gender, will be summarized, as well as which previous Novan study the subject was enrolled in (NI-AC301 or NI-AC302) and previous treatment assignment (SB204 or Vehicle).

For female subjects the following summaries will be included: child-bearing potential, contraceptive use at baseline. Medical history will be summarized for each treatment group by SOC and PT and presented in listings. Adverse events ongoing at end of pivotal study will be carried forward to this study, will not be considered treatment-emergent for this study, and will be summarized separately by SOC, PT, and relatedness.

### 4.4 Extent and Duration of Exposure

Summaries of the duration of exposure, days of exposure, and extent of exposure (calculated total grams) to study drug will be presented, overall and by whether previously randomized to SB204 (SB204 experienced) or randomized to Vehicle (SB204 naïve). This information plus study drug management details will be listed as well. All exposure endpoints will take into account whether the subject received SB204 in the previous study (NI-AC301 or NI-AC302).

Duration of exposure will be defined as:

Date of Last Drug Administration – Date of First Drug Administration + 1 day

Where date of first drug administration is the date of first treatment in the previous pivotal study for subjects randomized to SB204 in the previous study, and date of first dose in the LTS for subjects randomized to vehicle in the previous study.

Days of exposure will be defined as the total number of days that the subject reported taking study medication, and includes the days of exposure to SB204 in the previous study (NI-AC301 or NI-AC302) if applicable.

Extent of exposure will be based on the number of areas treated (face, upper back, and/or upper chest/shoulders, and any other areas reported) and the number of days with treatment. For subjects randomized to SB204 in the previous studies, drug was only applied to the face so for the days of exposure from the previous studies, it will be assumed that there is only one area of application, i.e. the face.

Each application is equal to 0.9 g. Extent of exposure is estimated as the sum of application areas (face only=1, face and chest=2, etc.) times the number of days of application to those areas times 0.9g. For example, a subject who applies 200 applications to the face only will have extent of exposure = 180g, while a subject who applies 100 applications to the face and 50 applications to the upper back will have extent of exposure = 135 g. The maximum extent of exposure would be: [0.9 grams x number of days on treatment in previous study] + [0.9 grams x 4 areas x number of LTS days on treatment]. Most subjects will have less exposure than this, so extent of exposure will be categorized logically depending on actual distribution of subjects. Initially, quartiles will considered.

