	Subjects will be assessed at each visit through Week 40 for cutaneous tolerability on the face. Tolerability will be assessed on a scale of 0 to 3 where 0=none, 1=mild, 2=moderate, and 3=severe for erythema, scaling, dryness, pruritus, and burning/stinging. The body surface area (BSA) treated (based on locations) will be collected at each visit for each subject Extent of exposure will be calculated for each subject based on the number of treatments and treatment area. Extent of exposure will also be summarized on a unit day which will be defined as total exposure divided by the total number of days enrolled.
Endpoints	Safety endpoints will include adverse events, changes in physical
	examination and changes in vital sign measurements. Any clinically significant changes noted during the physical exam as well as from the vital sign measurements will be recorded as adverse events and included in the comparison. Urine pregnancy tests in women of child-bearing potential will be conducted at each visit.
	Tolerability endpoints will include the investigator's assessment of erythema, scaling, dryness, and the subject's report of pruritus and burning/stinging based on the preceding 24 hours.
Statistical Methods	All statistical processing will be performed using statistical analysis software (SAS®) unless otherwise stated. Safety analyses will be performed using the safety population.
	Safety Analyses
	Adverse Events
	All AEs occurring during the study will be recorded and classified on the basis of the Medical Dictionary for Regulatory Authorities (MedDRA) terminology. Descriptions of AEs will include the date of onset, the date the AE ended, the severity of the AE, the relationship to study medication, and the outcome. All reported AEs that occurred on or after the Baseline date will be included in the summaries and analysis. Summaries will be presented to describe the characteristics of the adverse events reported and will include the number and percentage of subjects who report at least one AE and the number of events reported by severity, seriousness, and relationship to study medication. A
	summary of adverse event system organ class (SOC) and preferred terms (PTs) will also be presented. A subject will be counted only once under

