3. STUDY DESIGN

Figure 1 depicts the overall study design for this 40-week, open label study in subjects with acne vulgaris dosed once daily with SB204 4%. Subjects must have completed participation in one of the pivotal acne trials (NI-AC301 or NI-AC302) to be eligible to participate in this long term safety trial. Subjects will be treated chronically or repeatedly as recommended by the Investigator for up to 40 weeks. The Investigator may stop treatment if the subject's acne is in remission and re-initiate treatment if the subject's acne recurs. Any subject who is determined to be clear will remain enrolled in the study until study completion or termination. The total time on study will be counted as the days from enrollment until the subject discontinues or the study terminates.

Figure 1: Study Diagram

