3.1.3 EXTENT OF EXPOSURE

Extent of exposure will be calculated based on total number of days of study drug application and the body surface area treated (face, upper back, upper chest/shoulders).

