3.4 DOSAGE/DOSE REGIMEN

SB204 will be dispensed from a dual-chamber pump designed to deliver approximately equal amounts of NVN1000 Gel and hydrogel. NVN1000 Gel will be opaque and the hydrogel will be clear. The subject will instantly mix the two substances in the palm of the hand and then immediately massage a thin layer over the acne affected areas once daily after washing. The product should be mixed for about 5 seconds until thoroughly combined with a uniform opaque appearance then applied with the fingertips. Subjects should apply SB204 prior to bedtime.

Up to 2.7 g of SB204 4% will be applied evenly over the acne affected area, including the face, chest, back, and upper shoulders once a day for a period of up to 40 weeks (280 days). The amount of SB204 per application will vary depending on the areas to be treated as shown in Table 1 below. One pump stroke (0.9 g) will be used for the face. Application to the face, upper back and upper chest/shoulders will require up to 2.7 g (three (3) pump strokes).

Table 1: Dosing Amount by Area

Area (BSA)	Number of Pump Strokes	Amount of Product	
Face (3%)	1	0.9 g	
Upper Back (6%)	1	0.9 g	
Upper Chest/Shoulders (8%)	1	0.9 g	

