4.1.2 WEEKS 4, 12, 24 AND 36 (DAYS 28, 84, 168, 252)

The following procedures must be performed and recorded at the Weeks 4, 12, 24, and 36 visits:

- 1. Update concomitant medication information.
- 2. Update AE information and record any new AEs if applicable.
- 3. Obtain UPT (WOCBP only) and evaluate results.
- 4. Collect blood pressure and pulse rate after the subject has been sitting quietly for 5 minutes.

- 5. Perform cutaneous tolerability evaluation (face only).
- 6. Perform lesion counts (face only).
- 7. Record areas treated since last visit (face, upper back, upper chest/shoulders).
- 8. Collect returned study drug and diary, perform accountability, and review study drug compliance with subject.
- 9. Review subject diary for completion.
- 10. Dispense new study drug and diary.
- 11. Review and confirm the study schedule with the subject.

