7.7 EXTENT OF EXPOSURE

Extent of exposure will be based on days of treatment and the body surface area treated (face, upper back, and/or upper chest/shoulders) as collected at each visit for each subject. AEs will also be summarized by extent of exposure to determine if there is a safety signal due to duration of exposure or total body area exposed.

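### No planned adverse-event table shows treated body area as its own factor, although Protocol 7.7 names total body area as one of two exposure aims

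*SAP*

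**What the plan says.** **Protocol.** Section 3.1.3 bases extent of exposure on days of application and BSA treated. Section 7.7 repeats this and says why AEs are to be summarized by extent: "to determine if there is a safety signal due to duration of exposure or total body area exposed". Table 1 in Section 3.4 assigns 3% BSA to the face, 6% to the upper back and 8% to upper chest/shoulders, each with one 0.9 g pump stroke. On collection, the synopsis says: "The body surface area (BSA) treated (based on locations) will be collected at each visit for each subject". It adds a further exposure summary: "Extent of exposure will also be summarized on a unit day", defined as total exposure over days enrolled.

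**SAP.** Section 4.4 gives the extent rule: "Extent of exposure is estimated as the sum of application areas (face only=1, face and chest=2, etc.) times the number of days of application", multiplied by 0.9 g. Table 1 in Section 3.2 keeps a BSA column heading but no percentages, and lists upper chest and shoulders as separate areas. Section 4.5.1 plans AEs by windows of duration, with the stated purpose of finding a signal due to duration. It then plans AE incidence by gram category, with no stated purpose. The exposure-based AE shells, from Table 14.3.3.2.1 through Table 14.3.3.11.2, have either time-window or gram columns. Treated areas appear in Table 14.2.1 (ever or never treated, without AEs) and Listing 16.2.6 (by visit, without AEs). The unit-day summary appears nowhere in the SAP text, tables or listings.

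**The concern.** The Protocol asks two safety questions about exposure. The SAP gives duration its own tables, but area reaches the AE tables only inside a product of areas and days. A user of many areas who stops early and a face-only user who completes can share a gram category. Face and upper back cannot be told apart, because each counts as one area at 0.9 g.

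Area matters here because, by SAP 4.4, drug in the pivotal studies went only on the face, while this study allows up to 17% BSA. Cutaneous tolerability is scored on the face only (Protocol 4.1.2 and 4.1.3), so local reactions on the chest, back or shoulders will be captured mainly as AEs. Protocol 1.5 also lists hypotension and headache as theoretical risks of systemic exposure. Under the SAP as written, a reader asking whether AEs rise with treated area would have to merge two listings.

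**Working it through.** Inputs:
- 0.9 g per area per day, and extent = 0.9 × sum over areas of days applied (SAP 4.4).
- Up to 280 treatment days in this study (Protocol 3.4).
- For SB204-experienced subjects, 12 pivotal weeks = 84 days (Protocol 3.7.2), face only (SAP 4.4).
- BSA: face 3%, upper back 6%, upper chest/shoulders 8%, together 17% (Protocol Table 1).
- Gram columns 1-100, >100-330, >330-675 and >675 (mock Table 14.3.3.2.2). SAP 4.4 leaves the final cuts to the observed distribution.

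**1. The SAP's own examples.** 0.9 × 200 = 180 g and 0.9 × (100 + 50) = 135 g. Both reproduce.

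**2. One gram value, different areas.**

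| Use | Grams | BSA | %BSA-days |
|---|---|---|---|
| Face, 280 days | 0.9 × 280 = 252 | 3% | 3 × 280 = 840 |
| Upper back, 280 days | 0.9 × 280 = 252 | 6% | 6 × 280 = 1680 |
| Four SAP areas, 70 days | 3.6 × 70 = 252 | 17% | 17 × 70 = 1190 |

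If chest and shoulders share one stroke, as in Protocol Table 1, 17% BSA uses 2.7 g/day and reaches 252 g in 252/2.7 = 93.3 days. The overlap remains.

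**3. Days of treatment in this study that fall in the >100-330 g column (daily use).**

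| Areas | Naïve | Experienced (75.6 g brought in) |
|---|---|---|
| 1 | 112-280 | 28-280 |
| 2 | 56-183 | 14-141 |
| 3 | 38-122 | 10-94 |
| 4 | 28-91 | 7-70 |

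Among naïve subjects the >330-675 g column mixes two areas for 184-280 days, three for 123-250 and four for 92-187.

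**4. Area information the columns do carry.** The face-only maximum is 252 g (naïve) or 75.6 + 252 = 327.6 g (experienced). With the +7-day Week 40 window, the experienced maximum is 0.9 × 371 = 333.9 g. The two-area maximum is 504 g or 579.6 g. So >330 g in practice means more than one area, and >675 g means at least three. Both also mean longer treatment.

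**5. What the unit-day figure would add.** Its denominator is days enrolled, and under Protocol 3 "The total time on study will be counted as the days from enrollment until the subject discontinues or the study terminates". A four-area user who leaves at day 70 has 252/70 = 3.6 g/day, against 252/280 = 0.9 g/day for a face-only completer. It gives 0.9 g/day for back-only use as well, and for a four-area user treated on 70 of 280 enrolled days. It describes intensity of use but does not identify area or relate AEs to it.

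**The case against.** The strongest reply is that the SAP delivers what Protocol 7.7 plans: one composite extent measure built from areas and days, with AEs summarized by it. The Protocol promises no separate table by area, and a BSA × days measure would also mix area with time. The equal 0.9 g per area comes from Protocol Table 1, and the SAP is silent on area as an aim but does not disclaim it. All of this stands. It makes the point a gap against a stated aim, without showing breach of a promised table.

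A reader might infer three stronger things.

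*That no planned table separates area from duration.* This is too broad. The duration tables isolate duration, and Table 14.2.1 shows areas. What is missing is an AE table by area.

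*That the gram tables would hide or reverse an area signal.* The documents do not support this. It depends on when events occur and on whether subjects are placed by total grams or by grams at onset, which the shells do not state. A purely hypothetical case shows how much. Assume 600 subjects, half face-only and half four-area, half of each experienced, with AE discontinuation of 4% and 8% (12 and 24 stops), and one cut at 330 g. Four-area users pass 330 g after 330/3.6 = 91.7 days (naïve) or (330 − 75.6)/3.6 = 70.7 days (experienced). With stops spread evenly over 280 days, the share of four-area stops at or below 330 g is (91.7 + 70.7)/2/280 = 29.0%, or 6.96 of 24.
- Placed by total grams: 18.96/306.96 = 6.2% at or below 330 g, against 17.04/293.04 = 5.8% above.
- Placed by grams at onset, among subjects reaching each category: 18.96/600 = 3.2% against 5.8%, the correct direction.
- Placed by total grams with all stops after day 92: 4% against 8%, also correct. With all stops by day 70: 36/324 = 11.1% against 0%.

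None of these rates or timings is in the documents, so no size of bias should be claimed.

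*That the missing unit-day summary is part of the same failure.* It is a separate, minor omission. It stands only in the synopsis and concerns exposure, not AEs.

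**Conclusion.** The point holds in limited form and should be acted on. Protocol 7.7 names total body area exposed as an aim, and no planned AE table addresses it as its own factor. The firm measure of the problem is the overlap: with daily use, one value, 252 g, covers 3%, 6% and 17% BSA, and the >100-330 g column can hold users of one to four areas. Against that, the upper columns do identify multi-area users, assuming at most 84 + 280 days apart from small visit-window effects. The listings would also allow an area review after the fact, though none is planned. Whether an actual signal would be diluted, reversed or shown correctly cannot be determined from the documents.

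**What to change.** 1. **SAP 4.5.1:** restore total body area exposed as an aim of the AE-by-exposure summaries.
2. **SAP 4.4:** derive BSA treated per visit interval from Protocol Table 1: face including jaw/neck 3%, upper back 6%, upper chest/shoulders 8% counted once. Note that 8% is an upper bound if only one of those two sites is treated.
3. **Tables:** add descriptive versions of Tables 14.3.3.2, 14.3.3.3 and 14.3.3.6 (TEAEs, related TEAEs, discontinuations) by BSA in the interval containing AE onset. Use 0% or off treatment, 3%, 6-9% and 11-17%, with Other sites that are not jaw or neck shown separately. The off-treatment column is needed because Protocol 3 lets treatment stop in remission while the subject stays enrolled.
4. **Denominators:** use person-days in each BSA category as the main one and subjects ever in that category as the second. A subject may count in more than one column.
5. Keep the gram tables as supportive.
6. Separately, and as a minor point, add unit-day exposure (grams in this study divided by days enrolled) to Table 14.2.1.

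The cost is three extra shells and a few derived variables, from data already recorded. Large-area columns may be sparse. The 6-9% group pools back only (6%), chest/shoulders only (8%) and face plus back (9%). Area is known per interval of up to 12 weeks, not at onset. Treated area is also confounded with acne extent, because the Investigator identifies the areas (SAP 3.1). The tables should therefore be labelled descriptive.

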application-site reactions may occur due to the active agent (NVN1000) or the vehicle. In other development programs, local application-site reactions that led to treatment discontinuations were observed following application of alcoholic NVN1000 Gel or Vehicle Gel under occlusion in subjects with psoriasis or to the genital/perianal area in subjects with genital/perianal warts.

Based on available data, Novan anticipates that the risks to subjects enrolling in this Phase 3 study at which the maximum strength of SB204 will be 4% once daily on up to 17% body surface area are minimal, and that appropriate monitoring is in place to assess safety. Some subjects may have a clinical benefit in this long-term, open label study.

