### 2.3 Extent of Exposure

Duration, days of, and extent of exposure for each subject will be determined based on the stop and start dates of use of SB204, the total number of days of study drug application, and the areas treated (face, upper back, upper chest, and shoulders).

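### The SAP counts upper chest and shoulders as two 0.9 g applications, where the protocol gives them one shared stroke under a 2.7 g daily cap, and it does not acknowledge the difference

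*SAP*

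**What the plan says.** Protocol 3.4 sets the daily amount: "Up to 2.7 g of SB204 4% will be applied evenly over the acne affected area, including the face, chest, back, and upper shoulders". It repeats the limit by strokes: "Application to the face, upper back and upper chest/shoulders will require up to 2.7 g (three (3) pump strokes". Protocol Table 1 has three rows (face, upper back, upper chest/shoulders), each with one stroke of 0.9 g. The same three-part division defines extent of exposure in Protocol 3.1.3, "the body surface area treated (face, upper back, upper chest/shoulders", and data collection in Protocol 4.1.2, "Record areas treated since last visit (face, upper back, upper chest/shoulders".

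SAP Table 1 has four rows. Upper chest and shoulders are separate, each with one stroke and 0.9 g. SAP 3.2 assumes one stroke is likely per area, and its 2.7 g example covers face, upper back and upper chest without shoulders. It lets jaw and neckline share the face stroke but has no matching rule for shoulders and chest. SAP 4.4 computes grams as areas times days times 0.9 g, and the long-term-study part of its maximum is "0.9 grams x 4 areas x number of LTS days on treatment". The shells for Table 14.2.1 and Listing 16.2.6 also show upper chest and shoulders separately.

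**The concern.** The protocol and the SAP assign different amounts of drug to the same pattern of use. Grams are a planned exposure summary. They also form the columns of ten treatment-emergent adverse-event tables (the tables ending in .2, from 14.3.3.2.2 to 14.3.3.11.2). Protocol 7.7 gives the purpose of summarising adverse events by exposure: "to determine if there is a safety signal due to duration of exposure or total body area exposed".

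If subjects followed the protocol, the SAP rule adds drug that was never applied, and only for those who treat both chest and shoulders. Those subjects would be grouped with others who used more product. If subjects instead used a separate stroke for each site, the grams are right, but treating all four sites then exceeds the protocol's daily cap, and nothing in the SAP records that.

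**Working it through.** **Inputs.** 0.9 g per stroke; 280 days (Protocol 3.4); visits at days 28, 84, 168, 252 and 280 (Protocol Table 2); shell cut points 100, 330 and 675 g (Table 14.2.1). Assumption: 12 × 7 = 84 face-only days in the pivotal study for experienced subjects.

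**The plan's own figures.** Protocol maximum: 3 × 0.9 = 2.7 g/day, as stated. SAP 4.4 examples: 200 × 0.9 = 180 g and (100 + 50) × 0.9 = 135 g, both as stated. SAP maximum: 4 × 0.9 = 3.6 g/day. This figure is not printed but follows from the formula; 3.6 / 2.7 = 1.33.

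**Excess if dosing followed Protocol Table 1.** It is 0.9 g per treated day with both sites counted. By visit interval at full adherence:
- 28 days: 25.2 g
- 56 days: 50.4 g
- 84 days: 75.6 g

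Over the study, 28 + 56 + 84 + 84 + 28 = 280 days and 0.9 × 280 = 252 g.

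**SB204-naïve subject, 280 treated days (grams = 0.9 × strokes × 280):**

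| Sites treated | Protocol rule | SAP rule | Difference |
|---|---|---|---|
| Face, back | 504 | 504 | 0 |
| Face, back, chest | 756 | 756 | 0 |
| Chest, shoulders | 252 | 504 | +100% |
| Face, chest, shoulders | 504 | 756 | +50% |
| All four | 756 | 1008 | +33% |

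The grouping changes whatever cut points are used. Face, chest and shoulders ties with face and back under the protocol rule, but with face, back and chest under the SAP rule.

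**Experienced subject, adding 0.9 × 84 = 75.6 g.** Face, chest and shoulders: 579.6 against 831.6 g (+43%). All four: 831.6 against 1083.6 g (+30%).

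**Shell categories.** Face, chest and shoulders moves from >330-675 g to >675 g for both subject types above. A naïve subject treating all sites is above 675 g at 280 days under either rule. With fewer treated days the rules can disagree: 675 / 3.6 = 187.5 and 675 / 2.7 = 250, so 188 to 250 treated days gives >675 g under the SAP rule only.

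**Study mean.** The share treating both sites is not given. The mean rises by at most 252 g × share: 25.2, 63.0 or 126.0 g at assumed shares of 10%, 25% or 50%.

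**The case against.** Several points on the other side have weight.

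- **The four areas may be a different four.** SAP 4.4 also lists face, upper back, upper chest/shoulders combined, and any other reported area. That is four items, so a reader should not infer that SAP 4.4 certainly contradicts itself. But on that reading SAP Table 1 and the shells, which split chest from shoulders, conflict with SAP 4.4. A mismatch remains either way.
- **Separate strokes may really have been used.** SAP 3.2 states its one-stroke assumption openly, SAP 4.4 calls the grams an estimate, and Protocol 7.1 leaves detailed methods to the SAP. The subject instructions, diary and case report form are not among the documents. It is tempting to conclude that the reported grams are wrong, or that subjects were overdosed; neither can be shown. Even so, an assumption is not an explanation for exceeding 2.7 g/day.
- **Body surface area.** One might infer that four areas breach the limit in Protocol 1.5, "maximum strength of SB204 will be 4% once daily on up to 17% body surface area". They do not: splitting one region in two adds no skin. Nor does a plain list of sites such as SAP 2.3, "the areas treated (face, upper back, upper chest, and shoulders", show four-stroke counting, since Protocol 3.4 names similar sites under a 2.7 g cap.
- **Grams are not body area.** From Protocol Table 1, face and back cover 3 + 6 = 9%, and face with chest/shoulders 3 + 8 = 11%. The protocol stroke rule ties them at 504 g; the SAP rule separates them. The case for correction is therefore that grams should reflect drug applied, not that they would track area better.
- **The tables are descriptive, and the worked examples are right.** Both are true, so this is not an arithmetic error.

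**Conclusion.** The point holds as a protocol-SAP mismatch in a derivation rule, of low to moderate severity. The conflict over strokes and the daily cap does not depend on what subjects did; the overstatement of grams does.

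Given dosing by Protocol Table 1, the excess ranges from 0 for anyone using at most one of the two sites to 252 g for a subject treating both on all 280 days. The upper end is a corner case, because Protocol section 3 lets the investigator stop treatment in remission and restart it. How many subjects would change category cannot be said: SAP 4.4 sets the categories from the actual distribution, so the shell cut points are provisional.

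A reader might infer that the study's safety conclusions are compromised. The documents do not support that. Overall adverse-event incidence, the severity tables, days of exposure and the duration-window tables do not use the stroke rule.

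**What to change.** State one area-to-stroke rule in SAP 3.2, SAP Table 1, SAP 4.4 and Listing 16.2.6:

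- Count upper chest and/or shoulders recorded in the same visit interval as one 0.9 g application per treated day, in parallel with the jaw/neck rule.
- Restate the maximum for the protocol's areas as [0.9 g × prior SB204 days] + [0.9 g × 3 areas × LTS days]. That is 756 g for a naïve subject over 280 days, or 831.6 g with an assumed 84 prior days.
- State that any other reported area, apart from jaw or neck, adds 0.9 g per treated day, and that on top of all three protocol areas this exceeds 2.7 g/day. Without this sentence the three-area figure would wrongly read as an absolute ceiling.
- Set the gram categories only after the rule is fixed.

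If subjects were instructed to use separate strokes for chest and shoulders, keep four areas and document the departure from the 2.7 g/day cap.

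The cost is SAP and shell wording plus one recoding rule applied to areas already planned for recording at each visit. No new data are needed.
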